### 6.6.2 Laboratory Data

Hematology and chemistry laboratory data were collected only for participants in Phase 1. For that reason, analysis of hematology and chemistry laboratory data will be done on Phase 1 SAS only.

The following parameters will be analyzed:

- Hematology: Hemoglobin, White blood cells, Platelets, Neutrophils, Lymphocytes
- Chemistry: Creatinine, Alanine transaminase, Aspartate transaminase, Total bilirubin, Gamma-glutamyl transferase, Alkaline phosphatase

Data will be analyzed according to the visit labels as collected. Assessments performed at unscheduled visits will be not included in summary tables but will be included in listings.

The actual value and change from Baseline to each visit where assessment was scheduled will be summarized for each hematology and chemistry parameter. Additionally, number and percentage of participants with abnormality (high/low) and with clinically significant result will be summarized at each visit.

Positive pregnancy test results will be provided in data listings.

A listing presenting the laboratory data of subjects with at least one abnormal laboratory values will be provided.

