Unsolicited AE reporting is less frequent following ARCT-021 as compared to solicited AEs. The most common unsolicited AEs in both studies include headache, fatigue, injection site tenderness, diarrhea, elevated CPK, neutropenia, lymphopenia, urticaria and hematuria (which was not confirmed on microscopy).

Overall, no trends for vaccine-related abnormalities were observed in ECGs (evaluated in the ARCT-021-01 study only) or vital signs following vaccination with ARCT-021. Other safety laboratory assessments with patterns of interest include declining hemoglobin values (most likely due to blood sampling during trial participation), slight shifts in potassium values, and slight shifts in lymphocyte and neutrophil count. These laboratory abnormalities have been asymptomatic, and the minority have been reported as clinically significant changes.

Transient, asymptomatic lymphopenia and neutropenia have been observed with other mRNA SARS-CoV-2 vaccines ([Mulligan 2020](#); [Sah 2021](#); [Sahin 2020](#); [VRBPAC 2020](#)), however, lymphopenia is thought to be a normal physiological response (innate immune-stimulation-related redistribution of lymphocytes into lymphoid tissues) to immune stimulation from the vaccine ([Sah 2021](#); [Sahin 2020](#)).

Immunogenicity results following vaccination with ARCT-021 showed a robust IgG immune response to the full-length SARS-CoV-2 spike glycoprotein at all doses evaluated. At doses $\geq 3 \mu\text{g}$, GMT for PRNT50 neutralizing antibody responses tested with a clinical isolate of SARS-CoV-2 were within the range of titers observed in convalescent plasma from COVID-19 patients tested in the same assay at the same laboratory. Spike-specific T-cell responses were observed in response to stimulation with peptides from the spike glycoprotein and the CD4+ response was Th1-dominant.

The evaluation of safety data across the hundreds of participants dosed with ARCT-021 demonstrates that the vaccine leads to mild to moderate, transient AEs following vaccination for the majority of individuals. Overall AE reporting may decrease with second vaccination.

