7.4.1.3.4 Laboratory Test Abnormalities

For participants in Phase 1, clinically significant abnormal laboratory test results, in the opinion of the Investigator, may constitute or be associated with an AE. Examples of these include abnormal laboratory results that are associated with symptoms or require treatment, e.g., bleeding due to thrombocytopenia, tetany due to hypocalcemia, or cardiac arrhythmias due to hyperkalemia. Whenever possible, the underlying diagnosis should be listed in preference to abnormal laboratory values as AEs. Severity grading of abnormal test results should follow the grading of unsolicited AEs when the event is deemed clinically significant by the Investigator (Section [7.4.1.1.2](#)). Clinically significant abnormalities will be monitored by the Investigator until the parameter returns to its baseline value or until agreement is reached between the Investigator and Sponsor Medical Monitor (or designee) that further follow-up is not required. Laboratory abnormalities deemed NCS by the Investigator should not be reported as AEs. Similarly, laboratory abnormalities reported as AEs by the Investigator should not be deemed

NCS on the laboratory sheet. Where relevant, safety laboratory assessments will be analyzed by toxicity grade at the time of interim and final analysis.

The Investigator is responsible for reviewing and signing all laboratory reports. The signed clinical laboratory reports will serve as source documents and should include the Investigator's assessment of clinical significance of out of range/abnormal laboratory values.

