### 6.6.3 Vital Signs and Physical Examinations

Vital Signs will be analyzed for the following analysis sets:

- Phase 1/2/3a SAS
- Phase 3b SAS
- Phase 3c SAS
- Pooled SAS

Vital signs measured include systolic and diastolic blood pressure, heart rate, and respiratory rate.

Data will be analyzed according to the visit labels as collected. Assessments performed at unscheduled visits will be not included in summary tables but will be included in listings.

The actual value and change from Baseline to each visit (pre-dose assessment, if dosing visit) where assessment was scheduled (including ET visit) will be summarized for systolic and diastolic blood pressure. Summary of post-dose measurements and changes from pre-dose measurement will be done for each time point where pre- and post-dose measurements were performed.

Systolic and diastolic blood pressure will be graded as shown in Table 9. Shift tables from Baseline to each visit and from pre-dose to post-dose will be done.

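### The SAP drops the protocol's toxicity-grade analysis of the Phase 1 safety laboratory data without recording the change, so abnormalities not reported as adverse events get no count by grade

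*SAP*

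**What the plan says.** Protocol 7.4.1.3.4 (Laboratory Test Abnormalities) states: "Where relevant, safety laboratory assessments will be analyzed by toxicity grade at the time of interim and final analysis". The same section sends abnormalities that the investigator judges clinically significant to the severity grading used for unsolicited adverse events. It keeps those judged not clinically significant out of adverse event reporting.

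SAP 6.6.2 is the only laboratory analysis section and is limited to Phase 1. For continuous data: "The actual value and change from Baseline to each visit where assessment was scheduled will be summarized for each hematology and chemistry parameter". For categories, the "number and percentage of participants with abnormality (high/low) and with clinically significant result will be summarized at each visit", and nothing further is planned. On extra tests: "Assessments performed at unscheduled visits will be not included in summary tables but will be included in listings". It also promises individual data: "A listing presenting the laboratory data of subjects with at least one abnormal laboratory values will be provided".

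The next section, SAP 6.6.3, treats blood pressure differently. It assigns grades from Table 9 and adds: "Shift tables from Baseline to each visit and from pre-dose to post-dose will be done".

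SAP Sections 7.1 to 7.3 set out the changes from the protocol. None has an entry on laboratory data.

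**The concern.** Protocol 2.6 gives a reason to look at depth as well as direction. With the predecessor vaccine ARCT-021, neutropenia and lymphopenia were among the commonest unsolicited adverse events. The laboratory patterns of interest were falling hemoglobin, "slight shifts in potassium values, and slight shifts in lymphocyte and neutrophil count". A high/low flag gives a neutrophil count just under the limit the same weight as a very low one. It also flags a participant who was already low before the first dose.

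Only Phase 1 has scheduled safety laboratory tests. If these tables do not show how many participants moved to which grade, no other part of the trial can supply the answer.

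**Working it through.** The plan gives no figure to reproduce, so the check is mainly a comparison of text.

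**1. Commitment against plan.** The protocol promises analysis by toxicity grade, where relevant, at interim and final analysis. SAP 6.6.2 contains no grade, no shift from baseline and no worst post-baseline value. Section 7 of the SAP records changes as small as dropping confidence intervals for adverse event rates, but not this one.

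**2. Is the qualifier met?** Protocol 2.6 calls the ARCT-021 laboratory findings patterns of interest, and Protocol 2.7 expects the ARCT-021 experience to inform the safety profile of ARCT-154. Hematology grading is therefore plausibly relevant. If the sponsor thinks otherwise, the SAP does not say so.

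**3. What each kind of abnormality receives under the plan.**

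| Abnormality | Count by laboratory grade | What the outputs do show |
|---|---|---|
| Scheduled visit, clinically significant, reported as an adverse event | None | High/low and clinically significant counts, minimum/maximum, listing, adverse event severity |
| Scheduled visit, not reported as an adverse event | None | High/low count, minimum/maximum, listing |
| Unscheduled visit only, not reported as an adverse event | None | Listing |

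The minimum and maximum come from SAP 6.2.1, which prescribes them for all continuous variables.

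**4. How far the adverse event tables help.** Protocol 2.6 describes the ARCT-021 laboratory abnormalities as asymptomatic and says that a minority were reported as clinically significant. On that experience most findings would fall in the second row. For those that do become adverse events, Protocol 7.4.1.2.1 rates severity by effect on daily life, which does not measure how low a count fell. SAP 6.6.1.2 tabulates them in the Phase 1/2/3a safety set, and SAP 7.1 says safety will mostly not be repeated for Phase 1 alone. With planned ARCT-154 numbers of 75, 225 and 450:

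- one case among those with scheduled tests: 1/75 = 1.3%
- the same case in the pooled denominator: 1/(75 + 225 + 450) = 1/750 = 0.13%
- share of that denominator without scheduled safety tests: (225 + 450)/750 = 90%

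**5. What a minimum can and cannot show.** It gives the lowest scheduled count in each arm at each visit. It does not say how many participants were near that value or whether they began there. It is also an uneven comparison. If the vaccine had no effect, with complete data and no ties, the lowest of the 100 values would fall in the ARCT-154 arm with probability 75/100 = 75%.

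**6. New against pre-existing.** Phase 1 exclusion criterion 18 admits hemoglobin from 9.5 g/dL (women) or 10.5 g/dL (men), platelets from 100 x 10^9/L, and liver tests up to 1.5 times the upper limit. It sets no numeric limit for neutrophils or lymphocytes. Some participants may be flagged at baseline, and the per-visit counts do not separate them.

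**7. Is a scale available?** No. Protocol Table 19 (Appendix 4) covers solicited adverse events only, and SAP Table 9 covers blood pressure only.

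**8. Is the population defined?** SAP 6.6.2 uses a Phase 1 SAS. Protocol 8.2 lists one, but SAP 4.1 does not.

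**The case against.** The strongest reply is that little is hidden. Scheduled minima and maxima are tabulated, clinically significant results are counted, every participant with an abnormal value is listed, unscheduled results are listed, and clinically significant findings reported as adverse events carry a severity. Change from baseline and a randomized placebo arm give some protection against pre-existing abnormalities. Phase 1 also excludes clinically significant abnormal screening values. Laboratory values are not a component of the primary safety endpoint, and the protocol's sentence is qualified.

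All of that stands, and it rules out several stronger readings that a reader might infer:

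- *Severity is not reported at all.* Clinically significant cases reported as adverse events are tabulated by severity.
- *The tables could not reveal a severe cytopenia.* A very low scheduled count would set or approach the tabulated minimum.
- *Unscheduled results disappear.* They are left out of summary tables but listed. Nothing in the documents shows that the worst values would arise at unscheduled visits, though follow-up of clinically significant abnormalities makes repeat tests foreseeable.
- *The protocol requires grading without condition, or predicts neutropenia with ARCT-154.* The commitment applies where relevant, and the signal comes from the predecessor and from other mRNA vaccines.
- *Potassium and CPK were wrongly left out.* Neither document lists the contents of the chemistry panel, so their collection cannot be assumed.

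The reply does not supply a count of participants by grade, a baseline-to-post-baseline comparison of grades, or an entry in Section 7.

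**Conclusion.** The concern holds in this limited form: the SAP omits an analysis that the protocol committed to, with a qualifier, and does not record the omission. The consequence is that laboratory abnormalities not reported as adverse events have no count by grade, and new abnormalities are not separated from pre-existing ones in the per-visit counts.

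The reach is all scheduled safety laboratory data in the trial: 100 planned participants, 75 against 25, at Days 8, 29, 36 and 57. No primary conclusion depends on it, but it should be corrected because these are the only such data.

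The judgment assumes that at least the hematology parameters count as relevant under Protocol 7.4.1.3.4. It also relies on SAP Section 7 as a full account of what the previous SAPs changed, since those SAPs are not among the documents.

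**What to change.** In SAP 6.6.2:

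1. Name a laboratory toxicity grading scale, with its source, for the hematology and chemistry parameters already listed.
2. Add, by arm for the Phase 1 SAS, shift tables from baseline grade to each scheduled visit and from baseline grade to the worst post-baseline grade. Count unscheduled results in the worst grade.
3. Add potassium if it was part of the collected panel.

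In SAP 4.1, define the Phase 1 SAS. If the sponsor considers grading not relevant for some or all parameters, SAP Section 7 should say so and give the reason.

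The cost is SAP wording and a few extra tables on 100 participants, from data already collected. No new sampling is needed.

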### 6.6.3 Vital Signs and Physical Examinations

Vital Signs will be analyzed for the following analysis sets:

- Phase 1/2/3a SAS
- Phase 3b SAS
- Phase 3c SAS
- Pooled SAS

Vital signs measured include systolic and diastolic blood pressure, heart rate, and respiratory rate.

Data will be analyzed according to the visit labels as collected. Assessments performed at unscheduled visits will be not included in summary tables but will be included in listings.

The actual value and change from Baseline to each visit (pre-dose assessment, if dosing visit) where assessment was scheduled (including ET visit) will be summarized for systolic and diastolic blood pressure. Summary of post-dose measurements and changes from pre-dose measurement will be done for each time point where pre- and post-dose measurements were performed.

Systolic and diastolic blood pressure will be graded as shown in Table 9. Shift tables from Baseline to each visit and from pre-dose to post-dose will be done.

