Study vaccine will be administered in an observer-blind fashion as described in Section [6.3](#). The second study vaccination of each series must be at least 28 days after the first study vaccination. For Phase 1 and 3b, the first Switchover vaccination (Day 92) must be at least 56 days (+30 days) after the second vaccination of the initial series. For Phase 2 and 3a, the 3rd vaccination with study vaccine must be at least 56 days (+30 days) after the second vaccination series.

After receipt of study vaccine in the initial series of vaccinations, the participant will remain under observation for at least 3 hours for Phase 1, and 30 minutes for Phase 3b, and until clinically stable. For Switchover vaccinations, participants in Phase 1 and Phase 3b will be observed for at least 15 minutes and until clinically stable. Participants in Phase 2 and 3a will be observed for at least 30 minutes and until clinically stable for vaccinations 1, 2, and 3 (Day 92) and for at least 15 minutes and until clinically stable for vaccination 4 (Day 120). During the post-vaccination observation period, the participant will undergo assessment of vital signs, body temperature, AEs, and concomitant medications prior to discharge from the clinic.

Should a participant experience a severe AE (including but not limited to hypersensitivity or anaphylaxis) immediately following study vaccine administration, the participant should be observed until clinically stable, and the Clinical Research Organization (CRO) Medical Monitor should be notified immediately. Additional evaluation or testing may be performed based on

discussion between the Medical Monitor and the investigator and subject to Medical Monitor approval.

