APPENDIX 2: CASE DEFINITIONS OF COVID-19

Primary Case Definition (Based on FDA recommendation (DHHS 2020))

Case Definition	Laboratory Finding*	Clinical Status	
		Symptoms	Other Clinical Parameters
Uninfected	No positive SARS-CoV-2 test	None	None relevant
Asymptomatic SARS-CoV-2 Infection	Positive SARS-CoV-2 test	None	None relevant
Protocol-defined COVID-19	Positive SARS-CoV-2 test	At least one of the following that is a NEW or WORSENING finding: 
• Fever or chills• Cough• Shortness of breath or difficulty breathing• Fatigue• Muscle or body aches• Headache• New loss of taste or smell• Sore throat• Congestion or runny nose• Nausea or vomiting• Diarrhea	None relevant
Atypical COVID-19	Positive SARS-CoV-2 test	Clinical findings suggestive of COVID-19 but not included in the row above	None relevant
Severe COVID-19	Positive SARS-CoV-2 test	As above for protocol-defined COVID-19	Any of the following: 
• Clinical signs at rest indicative of severe systemic illness:
- Respiratory rate ≥ 30 per minute,

Case Definition	Laboratory Finding*	Clinical Status	
		Symptoms	Other Clinical Parameters
			
- Heart rate ≥ 125 per minute,- $\text{SpO}_2 \leq 93\%$ on room air at sea level or $\text{PO}_2/\text{FiO}_2 < 300$ mm Hg• Respiratory failure (defined as needing high flow oxygen, noninvasive ventilation, mechanical ventilation or ECMO)• Evidence of shock:
- $\text{SBP} < 90$ mm Hg, or- $\text{DBP} < 60$ mm Hg,- or requiring vasopressors• Significant acute renal, hepatic, or neurologic dysfunction• Admission to an ICU• Death

Abbreviations: COVID-19=coronavirus disease 2019; DBP=diastolic blood pressure; ECMO=extracorporeal membrane oxygenation; FiO_2 =fraction of inspired oxygen; ICU=intensive care unit; pO_2 =partial pressure of oxygen; SARS-CoV-2=severe acute respiratory syndrome coronavirus 2; SBP=systolic blood pressure; SpO_2 =oxygen saturation

Alternate Case Definition for Grading of Severity of SARS-CoV-2 Infection/COVID-19 (Based on World Health Organization WHO 2020)

Case Definition	Lab Finding*	Clinical Status	Other Clinical Parameters	Score
Uninfected	No positive SARS-CoV-2 test	N/A	N/A	0
Mild Disease	Positive SARS-CoV-2 test	Ambulatory	Asymptomatic	1
			Symptomatic; independent	2
			Symptomatic; assistance needed	3

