**Table 9 Vital Signs Toxicity Grading Scales**

	Systolic Blood Pressure (mmHg)	Diastolic Blood Pressure (mmHg)
Normal	≤ 140	≤ 90
Grade 1	141-150	91-95
Grade 2	151-155	96-100
Grade 3	> 155	> 100

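### SAP Table 9 grades blood pressure upward only, so the planned shift tables class every low reading as Normal and cannot count low blood pressure by arm.

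*SAP*

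**What the plan says.** SAP Section 6.6.3 lists the measurements: "Vital signs measured include systolic and diastolic blood pressure, heart rate, and respiratory rate". It then plans three kinds of output.

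- **Change from baseline.** Values and changes at each visit "where assessment was scheduled (including ET visit) will be summarized for systolic and diastolic blood pressure".
- **Around dosing.** "Summary of post-dose measurements and changes from pre-dose measurement will be done for each time point" at which both measurements were taken. This sentence names no parameter.
- **Grades.** "Systolic and diastolic blood pressure will be graded as shown in Table 9", followed by "Shift tables from Baseline to each visit and from pre-dose to post-dose will be done".

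Table 9, titled "Vital Signs Toxicity Grading Scales", has four rows:

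| Category | Systolic (mmHg) | Diastolic (mmHg) |
|---|---|---|
| Normal | ≤ 140 | ≤ 90 |
| Grade 1 | 141-150 | 91-95 |
| Grade 2 | 151-155 | 96-100 |
| Grade 3 | > 155 | > 100 |

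The table shows no sign of a lost row or redaction. Protocol Section 4.5.3.2 supplies the post-dose data: in the observation period after each vaccination, "the participant will undergo assessment of vital signs, body temperature, AEs, and concomitant medications prior to discharge from the clinic".

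**The concern.** The scale is presented as a toxicity scale and its lowest row is labelled Normal, but that row has no floor. A markedly low reading therefore receives a label that is wrong for it, and the pre-dose to post-dose shift table is blind in one direction. Low pressure is a change one would want to see shortly after an injection. Protocol Section 4.5.3.2 itself mentions hypersensitivity and anaphylaxis as severe events that may immediately follow vaccination.

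The one-sided scale also differs from how the documents treat related data. SAP Section 6.6.2 tabulates Phase 1 laboratory abnormality in both directions, high and low. Protocol Appendix 2 lists low systolic or diastolic pressure under "Evidence of shock" in the severe COVID-19 definition, so low pressure is treated as clinically relevant elsewhere. Neither SAP Section 6.6.3 nor the list of changes in SAP Section 7 explains why the scale runs upward only.

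At stake is whether a reader of the graded safety tables can tell how many participants in each arm had low pressure after a dose.

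**Working it through.** The plan gives no figure to reproduce. The check applies the Table 9 cut-points to readings and then asks whether another planned output supplies the missing count.

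**1. Grading rule.** For systolic pressure: Normal if ≤ 140, Grade 1 if ≤ 150, Grade 2 if ≤ 155, otherwise Grade 3. For diastolic pressure the cut-points are 90, 95 and 100.

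**2. Low values.** Every whole-number systolic value from 40 to 89 and every diastolic value from 20 to 59 was graded. All came out Normal.

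**3. Illustrative pre-dose to post-dose changes.**

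| Pre-dose | Post-dose | Systolic shift | Diastolic shift |
|---|---|---|---|
| 120/75 | 118/74 | Normal to Normal | Normal to Normal |
| 120/75 | 80/45 | Normal to Normal | Normal to Normal |
| 145/92 | 80/45 | Grade 1 to Normal | Grade 1 to Normal |
| 153/98 | 85/50 | Grade 2 to Normal | Grade 2 to Normal |
| 160/105 | 70/40 | Grade 3 to Normal | Grade 3 to Normal |

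A trivial change and a large fall share a cell (first two rows). By the same rule a systolic fall from 145 to 84 is Grade 1 to Normal.

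**4. Do the continuous summaries supply the count?** SAP Section 6.2.1 gives mean, median, standard deviation, quartiles, minimum and maximum.

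- The minimum shows the single lowest value per group and time point, not how many participants had one.
- The lower quartile does not reveal falls confined to a few participants.
- The mean moves by −(size of fall × proportion affected). As an assumption not taken from the documents, let a 40 mmHg fall occur in a fraction of the roughly 8,000 participants per arm in Phase 3b:
  - 0.1%: 8,000 × 0.001 = 8 people; mean shift −40 × 0.001 = −0.04 mmHg
  - 0.5%: 8,000 × 0.005 = 40 people; mean shift −40 × 0.005 = −0.2 mmHg
  - 1%: 8,000 × 0.01 = 80 people; mean shift −40 × 0.01 = −0.4 mmHg

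Shifts of this size would not draw attention, so the continuous output does not replace a count.

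**The case against.** The strongest reply is that nothing of clinical weight depends on Table 9.

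- **Adverse event reporting is broad.** Protocol Section 7.4.1.1.1 has investigators report all adverse events whatever their clinical significance. Section 7.4.1.2 brings in safety-relevant events found from study data, naming vital signs.
- **The observation period is covered.** Under Protocol Section 7.4.1.1.4, an event in the 30-minute observation period that needs treatment or longer observation is a medically attended event. SAP Section 6.6.1.3 tabulates these. SAP Section 6.6.1.1 tabulates solicited reactions within 30 minutes, and dizziness is a solicited term.
- **The readings remain visible** in the continuous summaries and in listings.
- **Vital signs are not among the primary safety endpoints.**

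All of this stands. A reader might infer that hypotensive events would go unreported, or that the shift tables are the only objective check. The documents do not support either inference. One route does turn on judgement: Protocol Section 7.4.3 ties reporting of a changed vital-sign value to clinical significance. An asymptomatic low reading may therefore reach only the minimum and the listings.

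A reader might also infer that heart rate and respiratory rate are measured but never summarised. Only the baseline-change sentence and the grading are limited to blood pressure. The pre- to post-dose sentence names no parameter and may include them, so the text is unclear rather than exclusionary.

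Finally, the Appendix 2 shock values might look like ready-made limits. They belong to a case definition that also requires a positive test and symptoms, and nothing in the documents supports them as post-vaccination cut-offs.

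**Conclusion.** The point holds as a defect in the graded display. As written, every low reading is Normal in every shift table, in every phase and arm, and no planned output counts participants with low readings by arm. This follows directly from the cut-points and needs no assumption. The mean-shift illustration does rest on an assumed fall and assumed rates, and it shows only that the continuous summaries do not fill the gap.

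The reach is limited. No efficacy, immunogenicity or primary safety endpoint changes, and no adverse event table is affected. The number of participants concerned cannot be estimated from the documents. A move from Grade 1 to Normal might be read as improvement, but the SAP attaches no such interpretation; the problem is the label and the empty low side of the table. It should be corrected because the stated rule gives a wrong label and the remedy is cheap.

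**What to change.** - Add a pre-specified Low category to Table 9 for systolic and diastolic pressure, so that Normal has a lower bound. The sponsor should set and justify the limits; the Appendix 2 values are only an in-document reference point.
- Use the extended scale in both sets of shift tables, baseline to each visit and pre-dose to post-dose, by arm.
- At minimum, if no Low category is added, rename Normal as *not elevated*, so that the table does not certify low readings as normal.
- State explicitly in SAP Section 6.6.3 that the pre- to post-dose summaries include heart rate and respiratory rate.

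The cost is one SAP table edit, one clarifying sentence and programming; no new data are needed. Some healthy participants with habitually low pressure will be classed Low, but the baseline or pre-dose column of the shift table will show that they started there. SAP Section 2.4 says some SAP authors had access to unblinded Phase 1/2/3a/3b data, so the limits should be fixed without looking at low readings by arm.
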